We propose a randomized clinical trial (RCT) with a pre and post questionnaire assessing two conditions: (1) standard-of-care brochure (control condition) and (2) the EE film (treatment condition). For those currently enrolled in the study (N=3) outcomes will be assessed with two post questionnaires, the first to assess intentions immediately after exposure to the study conditions and the second to assess lasting effects of the intervention on behavior one month later. The second questionnaire will primarily evaluate participants' disclosure attitudes and beliefs, intimate partner disclosure intentions, medical adherence intentions, disclosure behavior, adherence behavior and reported internalized stigma. However, for newly enrolled participants only one post questionnaire will be assigned. Therefore, after completing the pre-test, intervention, and immediate post-test, they will not complete a follow up questionnaire. Thus, instead of participating in two waves of data collection, newly enrolled participants will only participate in one wave of data collection.

Prior to beginning the study, researchers will conduct a manipulation check for the PSA to ensure it is yielding the intended effects. The pre-test of the PSA will be conducted with 15-30 research participants. For the manipulation check, participants will provide verbal consent in place of signed consent. Therefore, completing the pre and post-test questionnaires will serve as their agreement to study participation. Participants will either be randomly assigned to view the PSA or to the control condition in which no stimulus will be used. Study conditions will

Version 10.5.2018 Page 2 of 11

be randomly assigned based upon the dates of data collection. Participants viewing the PSA will complete a brief pre-stimulus questionnaire. Once completed, respondents will view a brief (30-60 seconds) PSA addressing key points displayed in the *90 DAYS* narrative. At the conclusion of viewing the PSA, participants will complete a brief post-test questionnaire. If assigned to the control condition, participants will only complete the brief post-test questionnaire. All participants in the manipulation check will be compensated \$25 for their participation in the manipulation check.

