current study (Jones, Lacroix, & Porcher, 2017; Mitchell & Petroll, 2012). Using data provided by the Centers for Disease Control and Prevention (CDC) and geographic information systems mapping, researchers will run Facebook advertisements in specific states, across the Southern U.S., that are identified to have moderate to increased prevalence of HIV among Blacks. In addition to using specific states, as carried out by other researchers, study investigators will set specific criteria to distinguish which Facebook users will be exposed to the ad (Jones, Lacroix, & Porcher, 2017). The inclusion criteria for the Facebook advertisements will include: Black women between the ages of 18-50 living within the Southern U.S. Similarly to those who receive the print or virtual flyer, participants recruited via Facebook will be able to click on the link in the advertisement to be redirected to the study's consent form. If they deem the study is a good fit for them, they will proceed by clicking the "next" button. Once they select "next", participants will complete the pre-test questionnaire, view one of the assigned stimuli, and complete the initial post questionnaire. Once all anonymous responses have been submitted, a randomized code will be provided to participants. Participants will be instructed to enter this randomized code along with their email address to receive compensation. Three weeks after completing the pre- and posttest questionnaire, participants will receive a reminder, via the provided email, to complete the follow up questionnaire. Similarly, to part one of the main study, once all anonymous responses are submitted, participants will receive a randomized code. They will be asked to enter the randomized code and their email address to receive their final compensation. Lastly, researchers will also request HIV servicing agencies to post the study flyer on their Facebook pages.

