The third recruitment strategy consists of using a Qualtrics panel. According to Qualtrics, "A market research panel, also known as an online sample, is a group of people recruited to respond to a survey. They are typically chosen from a prearranged pool of respondents who've agreed to be contacted by a market research service in order to respond to surveys." Employing the study inclusion/exclusion criteria, Qualtrics panel, recruits willing participants for study participation. Participants recruited via the Qualtrics panel will be compensated directly via Qualtrics. They will receive a \$50 gift card for their participation.

Across all forms of recruitment, study conditions will be randomly assigned via the Qualtrics system. Once a participant provides consent and is screened for study inclusion, participants will complete the pre-test questionnaire. After completing the pre-test questionnaire, respondents will be assigned to one of two study conditions. They will either be asked to view one of the following: a brochure on safe disclosure or the 90 DAYS film. Upon completing one of the interventions, participants will be asked to immediately complete the post-test questionnaire. For participants recruited outside of the Qualtrics Panel, once all anonymous responses are submitted, they will be directed to a separate link to enter their randomized generated code and email address. The purpose of the randomized code is to verify that the participant completed the study. The purpose of the email address for those currently enrolled is two-fold. Firstly, it will allow researchers to compensate participants with a virtual \$30 Amazon gift card. Secondly, it will allow researchers to provide a follow up email, within 3-4 weeks, containing the link to the second

Version 10.5.2018 Page 4 of 11

post-test survey. Participants will be compensated with a \$20 virtual Amazon gift card. Altogether, currently enrolled respondents in the main study (N = 3), will receive a total of \$50 for their participation in the study. After each data collection, participants will be reminded of their right to withdraw their responses from the study without penalty.

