For newly enrolled participants, whether recruited via Qualtrics, social-media, health agencies, or word-of-mouth, only one wave of data collection will occur. Once participants complete the pre-test, intervention, and immediate post-test, they will not be re-contacted 3-4 weeks later for a follow up post-test. Newly enrolled participants who complete one wave of data collection will also be compensated with a total of \$50 in e-gift cards; just as their counterparts who were enrolled in two waves of data collection.

For participants randomly assigned to the pamphlet only condition, an opportunity to view the short film will be available upon submitting their anonymous responses to the post test survey.

6) Data and Specimen Banking*

N/A

7) Data Management

To maintain participants' privacy, identifying information will be safely maintained in a secured password protected file that only study team members will have access to. The study will be administered using Qualtrics survey software. All quantitative data will be analyzed using SPSS 24 and Mplus.

8) Risks to Subjects

There are no physical risks anticipated with participation in this study. It is possible that participants may experience some stress in completing the questionnaire, and/or some inconvenience in the time taken to participate in the two waves of this study. A breach of confidentiality is also a potential risk, but measures will be taken to minimize that risk (please see confidentiality section below). Due to anticipating minimal risks, this study will not assess adverse effects.

9) Potential Benefits to Subjects

No direct benefit can be promised to you from being in this study.

10) Compensation

Participants in the PSA pre-test will be compensated \$25. Light refreshments or lunch will be served during PSA pre-test sessions. Currently enrolled participants in the main study will be compensated with virtual Amazon gift cards oppose to cash. Participants will receive \$30 for the first part of the main study and \$20 for the follow up questionnaire of

Version 10.5.2018 Page 5 of 11

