the main study. Due to only participating in one wave of data collection, newly enrolled participants will receive one payment. However, just as those currently enrolled, newly enrolled participants will also be compensated with \$50 via gift card. Altogether, all participants in the main study (current and new) will be compensated \$50 in virtual gift cards. Participants recruited via Qualtrics will be compensated directly through Qualtrics. They will be compensated the amount agreed upon by their provider, which will be a minimum of \$50 in Tango gift cards. Participants recruited via all other strategies will be compensated via email with a total of \$50 in Amazon e-gift cards.

11) Vulnerable Populations

Minors, prisoners and those unable to consent will be excluded from the study. Pregnant women will not be excluded from the study. This study is presumed to have minimal risk. No data will be collected regarding one's pregnancy or baby.

12) Setting

Participant referrals and onsite recruitment will take place at the UM HIV Clinics at Jackson Memorial Hospital as well as other HIV service providing agencies across the Southern U.S., such as the AIDS Healthcare Foundation (AHF), Care Resource, Big Bend Cares, Neighborhood Medical Center, and Bond Community Health Center. Lastly, virtual recruitment will be conducted via Facebook and Qualtrics panel.

The PSA manipulation check will be conducted in the University of Miami's Clinical Translational Science Institute room or on the 7th Floor of the Soffer Clinical Research Center (CRB; rooms 710N or 710Q) located at [name] and the Batchelor Childrens Research Institute, [name], 2nd floor conference room.

Paper data for the PSA manipulation check will be stored at in the principle investigator's office at [name]. All electronic data and audio/video recordings will be stored on the password protected computers of research team members responsible for data analysis.

The main study will be conducted virtually, via Qualtrics software.

13) Resources Available

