Statistical Analysis Plan

Investigating the Effectiveness of an Entertainment Education Short Film for Internalized HIV

Stigma Reduction, Intimate Partner Status Disclosure Intentions, and Antiretroviral Medical

Adherence Intentions: A Randomized Controlled Trial Among Black Women Living with HIV

in the Southern U.S.

ClinicalTrials.Gov Identifier: NCT03898063

February 15, 2021

Introduction: Purpose of the Statistical Analysis Plan (SAP)

The purpose of this Statistical Analysis Plan (SAP) is to detail the study objectives, study hypotheses and research questions, as well as the primary outcome measures and data analyses.

Study Overview

This randomized controlled trial was conducted among Black women living with HIV in the Southern U.S. between the ages of 18 and 50. The study examined the efficacy of a short entertainment education (EE) narrative in comparison to a standard brochure for primarily improving the following: HIV status disclosure intentions, internalized HIV-related stigma, and antiretroviral medical adherence. Once consented, all participants completed a pre-test survey. Upon completing the pre-test, using the randomization feature in Qualtrics, participants were randomly assigned to one of two study arms: 1) EE narrative or 2) Brochure. After viewing the EE stimulus or the brochure, participants immediately completed a post-test survey. The primary aim of the study is listed below.

Aim 1. To investigate the effectiveness of an EE intervention for decreasing internalized HIV-stigma and increasing HIV status disclosure intentions and medical adherence intentions among Black women living with HIV in the Southern U.S.

The hypotheses guiding this research study included the following:

H_{1a-c}: Participants in the EE condition will report: a) lower levels of internalized stigma; b) higher levels of disclosure intentions; c) higher levels of medical adherence intentions.

Data Collection Plan

Participants will be recruited via two primary methods. Firstly, Facebook advertisements will be deployed to recruit participants who meet the inclusion criteria. Secondly, participants will be recruited via a Qualtrics panel.

Statistical Methods

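### Does the three-week follow-up text for Facebook recruits in protocol section 5 require a change to the plan?

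*Protocol*

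**What the plan says.** Protocol section 5 takes Facebook recruits through the pre-test, the assigned stimulus, the first post-test and a code-and-email step for payment. It continues: "Three weeks after completing the pre- and posttest questionnaire, participants will receive a reminder, via the provided email, to complete the follow up questionnaire". A second code follows: "They will be asked to enter the randomized code and their email address to receive their final compensation".

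The rule for new participants is given in three other places:

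- The opening of section 5 keeps two post questionnaires for the 3 women already enrolled and adds that "for newly enrolled participants only one post questionnaire will be assigned".
- Near the end of section 5, for newly enrolled women, "whether recruited via Qualtrics, social-media, health agencies, or word-of-mouth, only one wave of data collection will occur", and "they will not be re-contacted 3-4 weeks later for a follow up post-test".
- Section 10 (Compensation): "Due to only participating in one wave of data collection, newly enrolled participants will receive one payment".

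The SAP's Study Overview has one assessment after exposure: "After viewing the EE stimulus or the brochure, participants immediately completed a post-test survey". Its Statistical Methods section names three primary variables for the ANCOVA without repeating the time point.

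**The concern.** Read alone, the Facebook paragraph tells staff to email new recruits again, survey them again and process a second payment step. The one-wave rule forbids each of these. The participants are women living with HIV, and section 8 lists breach of confidentiality as a risk, so it should be clear who is contacted again.

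There is also a possible route into the analysis. Section 5 says the second questionnaire covers internalized stigma, partner disclosure intentions and adherence intentions, which are the three primary variables. For any woman with two post questionnaires, each outcome could exist at two times, and the ANCOVA text does not say which is used. If follow-up had been intended for one recruitment route and not the others, the trial would have a different assessment schedule by route. That would be a matter of design, not of wording.

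**Working it through.** No stated sample size, power or error rate is involved, so the check is mainly a comparison of text.

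**Step 1. Who has a follow-up?**

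| Place | Follow-up applies to |
|---|---|
| Section 4 (reminder email) | Women currently enrolled |
| Section 5, opening | The 3 currently enrolled; one post questionnaire for new women |
| Section 5, Facebook paragraph | No limit stated |
| Section 5, after the panel paragraph (purpose of the email address) | Women currently enrolled, N = 3 |
| Section 5, closing rule | Not new women; social media is named |
| Section 10 | One payment for new women |

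Five statements agree and one carries no qualifier. The closing rule is the more specific text because it names the Facebook route and excludes re-contact outright. The Facebook paragraph fits an earlier two-wave design that was not fully edited out.

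**Step 2. Are there other remnants?** Yes. Section 8 still mentions two waves, section 17 still collects email addresses to schedule a second wave, and section 18 still has a follow-up reminder. The timing also varies within section 5: one month in the opening, three weeks in the Facebook paragraph, and 3-4 weeks in the passage on the email address. This pattern points to incomplete editing, not to a separate schedule for Facebook recruits.

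**Step 3. Does the money differ?** For two-wave women, $30 + $20 = $50. For new women recruited outside the panel, one payment of $50. The Facebook paragraph states no amounts. The conflict is over the number of steps, not the total.

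**Step 4. Can the primary comparison be affected?** Women are randomized after the pre-test and complete the post-test straight after the film or brochure. A reminder three weeks later comes after those values are recorded. Even if every Facebook recruit were re-contacted, the immediate post-test data would be the same in both arms.

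**Step 5. Could an analyst use the wrong time point?** The SAP mentions no second questionnaire, so its ANCOVA has only one post-test to refer to. Under the stated rule, second values exist for 3 women at most, and no analysis in the SAP calls for them.

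**The case for a change.** The strongest case for a change is that an instruction about re-contacting participants should not need inference. The Facebook paragraph is written in the future tense and describes how recruitment will run. It lacks the qualifier that sections 4, 5 and 10 use elsewhere. Correcting it would cost only a few words, and adding the time point to the ANCOVA text would cost one phrase.

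The textual part of this stands: the paragraph does contradict the closing rule, and the remnants in sections 8, 17 and 18 belong with it. Stating once to whom the follow-up text applies, with one timing, would be reasonable if the protocol were reissued.

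The claim of consequence does not stand. It supposes staff who read one paragraph and ignore the rule a page later that names their recruitment route. The SAP overview, dated after the protocol, describes conduct in the past tense with no follow-up wave. Its data collection section is in the future tense, so this is supportive but not conclusive. Nothing in either document shows that a new Facebook recruit was contacted again. The missing time point is a gap that any analyst would fill correctly from the SAP's own overview.

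**Conclusion.** This is a clerical inconsistency, and no change to the plan follows. The follow-up wording is left over from a two-wave design, and the rule that replaced it is explicit for the same recruits. The effect on the primary analysis is nil, because the outcomes are fixed at the immediate post-test before any reminder could be sent. Total payment outside the panel is $50 on either reading. A second questionnaire properly applies to 3 women out of a ceiling of 400.

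This rests on two assumptions: that the one-wave rule governs new participants, as sections 5 and 10 state, and that the ANCOVA uses the only post-test the SAP describes. If new Facebook recruits had in fact been surveyed twice, that would be a question of adherence to the protocol and of handling email addresses. The comparison of film with brochure at the immediate post-test would still be unaffected.

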Traditionally, Black women within the U.S. are a hard to reach population for research involvement (Jones, Lacroix, & Porcher, 2017). Literature suggests that Black women often experience an amalgam of barriers to research engagement such as: lack of transportation, need for a babysitter, and extensive caregiving responsibilities for loved ones (Webster et al., 2018). Considering this, the National Institutes of Health is strongly encouraging researchers to identify strategies that increase study participation among this demographic (Jones, Lacroix, & Porcher, 2017). For this reason, the current study will align with peer reviewed research and conduct the experimental sessions for the main study via the online Qualtrics platform (Jones, Lacroix, & Porcher, 2017). All responses to questionnaires will be anonymous.

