Due to the sensitive and hard to reach nature of this study population, multiple recruitment strategies will be implemented. Firstly, a two-step recruitment process will be employed. Based upon the inclusion and exclusion criteria, clinic staff throughout the Jackson Health System as well as other HIV service providers across the state of Florida, will inform patients of the study via print and virtual flyers, sent via email. Dependent upon the study schedule, research team members maybe stationed at recruitment sites to speak with interested patients who desire further information. If research staff are not onsite, interested participants can contact the identified study team member listed on the recruitment flyer should they have further questions. All virtual flyers will be sent by clinic staff via a restricted email server to patients who have agreed to be contacted via email by their health provider. For patients who receive a printed or virtual copy of the study flyer, if they are interested in participating, they will visit the Qualtrics link provided on the flyer. Once they are on the study site, participants will read the consent form which thoroughly outlines the study's purpose, inclusion criteria, risks, benefits, compensation, voluntariness, and researchers' contact information. Should participants decide the study is a good fit for them, they will be able asked to consent by clicking the "next" button. Upon clicking the "next" button participants will be asked screening questions based upon the study's inclusion criteria (See updated measures guide). Once screened, if participants meet the eligibility requirements they will be guided through the study. Should participants not meet the eligibility criteria, they will be redirected to the end of the study and thanked for their time. Participants will be fully aware via the consent form that they can withdraw from the study at any time.

The second recruitment method will consist of paid targeted Facebook advertising. This recruitment strategy has yielded successful results in similar populations as the

Version 10.5.2018 Page 3 of 11

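### Does the online main study need a check that the film or brochure was viewed, and a planned report of viewing by arm?

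*Protocol*

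**What the plan says.** Protocol section 12 (Setting) fixes the mode of delivery: "The main study will be conducted virtually, via Qualtrics software". Section 5 (Procedures Involved) describes the exposure step after randomisation: "They will either be asked to view one of the following: a brochure on safe disclosure or the 90 DAYS film". The next step is the outcome assessment: "Upon completing one of the interventions, participants will be asked to immediately complete the post-test questionnaire". No criterion for having completed the stimulus is given.

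Section 5 also provides a completion code for women recruited outside the Qualtrics panel: "The purpose of the randomized code is to verify that the participant completed the study". It is used to release compensation. On later contact, section 5 states "All responses to questionnaires will be anonymous" and, for newly enrolled women, "Once participants complete the pre-test, intervention, and immediate post-test, they will not be re-contacted 3-4 weeks later".

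The screening questions are placed in a separate document, cited as "inclusion criteria (See updated measures guide"). That guide and the questionnaires are not part of the protocol or SAP.

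The SAP (Study Overview) reports exposure as something that happened: "After viewing the EE stimulus or the brochure, participants immediately completed a post-test survey". Its Statistical Methods section names one analysis, an ANCOVA adjusted for age, on internalised stigma, disclosure intentions and adherence intentions. It mentions no viewing summary.

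**The concern.** The intervention is a single remote exposure, and no member of staff is described as observing it. A participant might click past the film or brochure and still submit a post-test. Newly enrolled women are seen in one session only, so viewing not captured then cannot be recovered later.

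Two features that might seem to answer the point do not. The code shows that the study was completed, not that the stimulus was seen. The manipulation check in Protocol section 5 concerns a 30-60 second PSA tested beforehand in 15-30 women, not the film or the brochure.

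What would be at stake is the reading of a null or small effect. Unwatched films pull the contrast towards zero. If the brochure itself has an effect, unread brochures widen the contrast. One stimulus is a film and the other a brochure, so non-viewing could differ between arms.

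**Working it through.** The documents give no power calculation, effect size, SD or viewing rate, so there is no planned figure to reproduce. The arithmetic asks only what a viewing check could change.

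**Inputs**
- 400 women: the ceiling for the main study in Protocol section 16.
- Assumed: 1:1 allocation (200 per arm), SD 1, no precision gain from the age covariate, two-sided 5%.
- Assumed: a share q of the film arm does not view and responds like controls.

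**1. The primary comparison.** The standard error of the difference is √(2/200) = 0.100, and the 95% half-width is t(0.975, 398) × 0.100 = 0.1966 SD. With an estimate of 0, the upper limit for the effect of assignment is 0.197 SD. Viewing data do not enter this calculation, so it is the same with or without a check.

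**2. The effect in viewers.** Under the assumption above, this effect is the contrast D divided by (1 − q), with approximate variance

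SE(D)²/(1 − q)² + D² × Var(q)/(1 − q)⁴.

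At D = 0 the second term vanishes, so sampling error in a measured q contributes nothing to this approximation. The upper limit is 0.1966/(1 − q):

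| Assumed q | Upper 95% limit for viewers (SD) |
|---|---|
| 0% | 0.197 |
| 10% | 0.218 |
| 20% | 0.246 |
| 30% | 0.281 |
| 50% | 0.393 |

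If 40 of 200 were recorded as non-viewers, the limit would be 0.1966/0.8 = 0.246 SD. Without a record, a reader has to choose q, and the width of the range depends wholly on that choice. Even with a record, the figure holds only as far as page time or recall tracks viewing, and only if non-viewers do respond like controls.

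**3. Power.** By the normal approximation, 80% power at 200 per arm corresponds to a difference of (1.960 + 0.842) × 0.100 = 0.280 SD. With film-arm non-viewing q, the difference becomes 0.280 × (1 − q) and power is Φ[0.280 × (1 − q)/0.100 − 1.960]:
- 10%: difference 0.252, power about 71%
- 20%: difference 0.224, power about 61%
- 30%: difference 0.196, power about 50%

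This is what non-viewing would cost. It is not the cost of leaving out a check: recording who did not view, with nobody excluded, leaves each of these figures where it is.

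**4. The text.** The SAP states its own scope as objectives, hypotheses, primary outcome measures and data analyses. A descriptive table of exposure falls outside that scope, and leaving it out does not alter any of the three planned comparisons.

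**The case for a change.** The strongest case for acting is that it would be cheap. While enrolment is open, passive page timing and two or three recall items placed after the primary scales would add little burden, could not affect those scales, and would give some basis for separating an ineffective film from an unwatched one. In a single anonymous session the chance does not return. Even if such items already exist, the SAP does not commit to reporting them.

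Much of this is true as description: the supplied text contains no viewing check and no planned report. Three things limit its force.
- Recall items would normally sit in the questionnaires, and page timing is a setting of the survey build. Since neither is available here, the most that can be said is that a check is not described.
- The separation it would buy is partial. Page time records elapsed time rather than attention. Aim 1 also asks about effectiveness, and for the effect of offering the film online, non-viewing is part of the answer. The Study Overview also uses the word efficacy, so this last point is not decisive.
- The SAP, dated February 2021, says in its Study Overview that the trial was conducted and the post-tests completed, although its recruitment and methods text is in the future tense. If data collection has closed, nothing can be added to the survey, and all that remains is a sentence in the report.

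**Conclusion.** No change to the plan. The observation is accurate within the supplied documents, but it concerns a descriptive detail that affects neither the validity nor the power of the primary analysis. The comparison by randomised arm stands, and keeping every randomised woman in it regardless of viewing is consistent with the plan as written.

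The benefit of a check is confined to interpretation. In the illustrative case it attaches a figure of about 0.246 SD to viewers, alongside 0.197 SD for assignment. That rests on 200 per arm, an estimate of zero, 20% film-arm non-viewing, non-viewers responding like controls, and a proxy that identifies viewing correctly. None of these comes from the documents except the ceiling of 400.

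This is a gap that analysts fill sensibly when they report. If timing or recall data were captured, they can be tabulated by arm beside the primary result. If they were not, saying that viewing was not measured is an ordinary limitation statement and needs no amendment.
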